9.1.2 Secondary Endpoints

Acute and late toxicity data will be tabulated by type, grade and dose level with the number, proportions and frequencies of grades 1-4 and grade 3-4 grades reported. The duration of clinical benefit assessed by overall response rate (ORR) defined as complete response (CR) or partial response (PR) and disease control rate (DCR) defined as CR, PR or stable disease (SD) using modified RECIST (Appendix 6) and RECIST 1.1 will be calculated as a proportion of total treated with a 95% confidence interval. Response rates (ORR and DCR), will be calculated as proportions for all patients and in the epithelioid and sarcomatoid histological sub-type giving associated 95% confidence intervals. Any difference in response rates (for ORR and for DCR) between the two sub-types will be compared using a chi squared or Fisher's exact test as appropriate. These will be evaluated for Part A and Part B and for overall. PD-L1 staining is referred to as tumour proportion score, reported as a percentage from 0–100%. It is classed as weakly positive (1 – 49%); strongly positive if >50%; and negative if <1%. The effect of PD-L1 expression on response rates will be measured using the proportion

of patients recorded to be weakly positive, strongly positive or negative and tested using a Chi Squared or Fisher's exact test for proportions on expression level between responders and non-responders. PFS will be measured from the start of radiotherapy until radiological or clinical evidence of progression or death and will be censored at date of last follow-up for surviving patients. OS will be measured from the start of radiotherapy until death and will be censored at date of last follow-up for surviving patients. Duration of response (DOR) will be measured from the date of first response until radiological or clinical evidence of progression or death and will be censored at date of last follow-up for surviving patients. Median PFS, OS and DOR will be calculated using Kaplan-Meier methods giving associated 95% confidence intervals, respectively. PFS, OS and DOR rates at 6 and 12 months will be presented with associated 95% confidence intervals. PFS, OS and DOR will be assessed for overall i.e. Part A and Part B combined. Unless otherwise stated, all secondary endpoints will be analysed for Part A, Part B and overall.

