3.2.2 Secondary Endpoints

- To assess acute toxicity rates (defined as up to 12 weeks after last SBRT fraction) using CTC AE v5.0.
- To assess late toxicity rates (defined as from 12 weeks after last SBRT fraction in MPM until 28 days after the last dose of pembrolizumab) using CTCAE version 5.0.
- To calculate the ORR, DCR and DOR using mRECIST and RESIST 1.1.
- To calculate the ORR and DCR in epithelioid versus sarcomatoid histological subtype using mRECIST and RESIST 1.1.
- To assess the frequency of PD-1/PD-L1 expression distribution in responders and non-responders.
- To measure the PFS and OS at 6 and 12 months.

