4.2.1 Dose Limiting Toxicities

Acute toxicity will be assessed up to and including 3 months following the final fraction of radiotherapy (i.e. at C6D1). The MRC dyspnoea score (Appendix 2) will be used to assess dyspnoea at baseline/on treatment and the Common Toxicity Criteria for Adverse Events (CTCAE) version 5.0 will be used to grade all drug and SBRT observed toxicities (Appendix 4). The SRC will consider expansion after the 6th patient in the initial safety cohort has completed the DLT period and reviewed the toxicities before recruitment to the expansion cohort Part B.

Any DLT must be a toxicity that is considered probably, possibly or definitely related to the combination of pembrolizumab and SBRT. DLT is defined as follows:

Haematologic:

- Neutropenia with fever grade 3 or neutropenia grade 4
- Thrombocytopenia with bleeding grade 3 or thrombocytopenia grade 4

Non-Haematologic:

Any ≥ 3 non-haematological toxicity which is definitely, probably or possibly related to the combination of pembrolizumab and SBRT for pleural mesothelioma including the following:

- Increased MRC dyspnoea score > 2 grades from baseline and/or acute dyspnoea grade ≥ 4 (or CTCAE dyspnoea grade ≥ 3) persisting for > 7 days (including weekend).
- Pneumonitis grade ≥ 3 persisting for > 7 days (including weekend).
- Oesophagitis grade ≥ 3 persisting for > 7 days (including weekend).
- Toxicity leading to interruption of radiotherapy for > 7 days (including weekend).

Progression of the study will not proceed until the following criteria are satisfied by the SRC:

- If 0 out of 3 patients experience a DLT, or if 1 out of 3 patients experience a DLT, a further 3 patients will be recruited at the dose level in the initial safety cohort.
 - If 0 out of 6 patients experience a DLT, or if 1 out of 6 patients experience a DLT, then progression to Part B of the study can proceed.
 - If ≥ 2 out of 6 patients (or more than 1 in the first 3 patients) experience a DLT, then there will be no Part B expansion phase and the study will be terminated.

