12.4 Appendix 4 - Common Terminology Criteria for Adverse Events V5.0 (CTCAE)

The descriptions and grading scales found in the Common Terminology Criteria for Adverse Events (CTCAE) version 5.0 will be utilized for AR reporting. (<http://ctep.cancer.gov/reporting/ctc.html>)

1. Quick Reference

The NCI Common Terminology Criteria for Adverse Events is a descriptive terminology which can be utilized for Adverse Event (AE) reporting. A grading (severity) scale is provided for each AE term.

2. Components and Organization SOC

System Organ Class, the highest level of the MedDRA hierarchy, is identified by anatomical or physiological system, etiology, or purpose (e.g., SOC Investigations for laboratory test results). CTCAE terms are grouped by MedDRA Primary SOCs. Within each SOC, AEs are listed and accompanied by descriptions of severity (Grade).

3. CTCAE Terms

An Adverse Event (AE) is any unfavorable and unintended sign (including an abnormal laboratory finding), symptom, or disease temporally associated with the use of a medical treatment or procedure that may or may *not* be considered related to the medical treatment or procedure. An AE is a term that is a unique representation of a specific event used for medical documentation and scientific analyses. Each CTCAE v5.0 term is a MedDRA LLT (Lowest Level Term).

4. Definitions

A brief definition is provided to clarify the meaning of each AE term.

5. Grades

Grade refers to the severity of the AE. The CTCAE displays Grades 1 through 5 with unique clinical descriptions of severity for each AE based on this general guideline:

Grade 1 Mild; asymptomatic or mild symptoms; clinical or diagnostic observations only; intervention not indicated.

Grade 2 Moderate; minimal, local or non-invasive intervention indicated; limiting age-appropriate instrumental ADL*.

Grade 3 Severe or medically significant but not immediately life-threatening; hospitalization or prolongation of hospitalization indicated; disabling; limiting self-care ADL**.

Grade 4 Life-threatening consequences; urgent intervention indicated.

Grade 5 Death related to AE.

6. Activities of Daily Living (ADL)

*Instrumental ADL refer to preparing meals, shopping for groceries or clothes, using the telephone, managing money, etc. **Self-care ADL refer to bathing, dressing and undressing, feeding self, using the toilet, taking medications, and not bedridden.

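### The acute and late toxicity rates in section 9.1.2 stop at grade 4, so a patient whose worst toxicity is fatal can be missing from both summary proportions

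*Protocol*

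**What the plan says.** The first two secondary endpoints in protocol section 3.2.2 are toxicity rates graded on CTCAE v5.0. One is acute: "To assess acute toxicity rates (defined as up to 12 weeks after last SBRT fraction) using CTC AE v5.0". The other is late: "To assess late toxicity rates (defined as from 12 weeks after last SBRT fraction in MPM", running until 28 days after the last pembrolizumab dose. Neither endpoint has an upper limit on grade.

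Section 9.1.2 gives the analysis. It begins with a tabulation, "Acute and late toxicity data will be tabulated by type, grade and dose level", and then fixes the summaries: "with the number, proportions and frequencies of grades 1-4 and grade 3-4 grades reported".

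Appendix 4 describes the scale: "The CTCAE displays Grades 1 through 5 with unique clinical descriptions of severity for each AE". Its last category is "Grade 5 Death related to AE".

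For the primary endpoint, the non-haematological DLT criterion in section 4.2.1 is open at the top: "Any ≥ 3 non-haematological toxicity which is definitely, probably or possibly related". Section 9.1.1 restricts the DLT proportion to Part A, and section 4.2 sets the DLT period at 12 weeks from the last SBRT dose.

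**The concern.** The endpoints use a five-grade scale, while the two summary rates use only its first four grades. Grade 5 belongs neither to 1-4 nor to 3-4, and no other section adds it to these rates or plans a separate proportion for fatal toxicity.

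The trial's primary objective is safety and tolerability. Readers are likely to take the grade 3-4 proportion as the rate of severe toxicity. As written, a patient with a fatal toxicity and no other severe entry contributes to that proportion exactly as a patient with no severe toxicity does. The bands are stated explicitly in the protocol, so an SAP that follows it would inherit them.

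**Working it through.** The protocol states no toxicity rate, so there is no planned figure to reproduce. The check compares definitions and then sizes the effect.

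**Inputs**
- Summary bands: grades 1-4 and 3-4 (section 9.1.2).
- Scale: grades 1 to 5 (Appendix 4).
- Planned numbers: 6 in Part A and 12 in Part B, 6 + 12 = 18 (sections 4.2 and 9.2). Section 9.1.2 does not name the denominator for toxicity, so I assume all planned patients. Section 5.3 supports keeping such a patient in: someone who stops for a drug-related AE is not replaced and stays in the evaluable population.
- Recording: section 8.2 collects the maximum CTCAE grade for each AE. Section 8.3.1 closes an AE when its grade changes and opens a new one at the new grade.

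**Step 1: who is missed.** Section 9.1.2 does not say whether the rates count every AE entry or each patient's worst grade. The answer depends on this.

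| Patient with a fatal toxicity | Counting every entry | Counting worst grade per patient |
|---|---|---|
| First recorded at grade 5, no other toxicity | in neither band | in neither band |
| First recorded at grade 5, other toxicity of grade 1-2 only | in 1-4, not in 3-4 | in neither band |
| Rose from grade 3 or 4 to 5, earlier entry kept under 8.3.1 | in both bands | in neither band |

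The severe rate therefore misses the patient in all three rows if worst grade is used, and in the first two rows if every entry is used.

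**Step 2: size for one missed patient.** Understatement = 1/n. Assume one patient with a grade 5 toxicity, no grade 3-4 entry counted for that patient, and no other patient with grade 3 or higher. I add exact binomial (Clopper-Pearson) 95% intervals for illustration; section 9.1.1 names the exact binomial interval for the DLT rate.

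| Set | Bands as written (3-4) | With grade 5 included (3-5) | Difference |
|---|---|---|---|
| Overall, n = 18 | 0/18 = 0% (0-18.5%) | 1/18 = 5.6% (0.1-27.3%) | 5.6 points |
| Part B, n = 12 | 0/12 = 0% (0-26.5%) | 1/12 = 8.3% (0.2-38.5%) | 8.3 points |
| Part A, n = 6 | 0/6 = 0% (0-45.9%) | 1/6 = 16.7% (0.4-64.1%) | 16.7 points |

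**Step 3: how often it could matter.** The protocol gives no fatal toxicity rate, so p is an assumption. The chance of at least one fatal toxicity in 18 patients is 1 − (1 − p)^18:
- p = 1%: 16.5%
- p = 2%: 30.5%
- p = 5%: 60.3%
- p = 10%: 85.0%

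**Step 4: does the primary endpoint cover the gap?** Only in part. Reading the threshold in section 4.2.1 as grade 3 or higher, a related non-haematological grade 5 event within 12 weeks of SBRT is a DLT and enters the Part A proportion. The 12 Part B patients have no DLT rate, and neither does the late window in any patient. There the section 9.1.2 bands are the only planned toxicity proportions.

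**The case against.** The strongest reply is that nothing of substance is lost. The sentence that sets the bands also tabulates toxicity by grade with no top grade, and section 9.1.1 does the same for all toxicities in Part A. A fatal event is an SAE reportable within 24 hours (sections 8.4 and 8.4.1), the Safety Review Committee reviews all SAEs (section 11.9), and deaths enter PFS and OS. Progression to Part B and early termination rest on DLT counts. All of this stands, and it limits the weight of the point. It does not put grade 5 into either summary proportion.

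A reader might infer more than the text supports:
- **That deaths disappear from the report.** They do not; only the two summary rates omit them.
- **That a death lowers the severe rate.** With a fixed denominator, a grade 5 patient leaves the grade 3-4 rate unchanged when it should rise. The understatement is at most 1/n per such patient.
- **That the recording rules guarantee exclusion.** Section 8.3.1 points the other way for an event that escalates, because the earlier grade 3 or 4 entry remains. Maximum intensity in section 8.2 is a field for each AE, not a rule for summarising patients.
- **That the DLT definition has no upper limit anywhere.** This is true of the non-haematological criterion. The haematological items name only grades 3 and 4.
- **That any disagreement between DLT and toxicity rates is an error.** The two differ by design, because a DLT must be related to the combination and the DLT rate is for Part A only.

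**Conclusion.** The point holds as an error in a stated rule. The bands in section 9.1.2 do not match the scale that the protocol adopts, and the endpoints in section 3.2.2 give no reason for stopping at grade 4.

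The effect is nil unless a fatal toxicity occurs. If one does, the size in the working rests on two assumptions: that the planned patient numbers are the denominators, and that no grade 3-4 entry for that patient is counted. The second turns on a counting convention that section 9.1.2 leaves open while fixing the bands.

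I rate it minor to moderate. It matters most for Part B and for late toxicity, where no DLT rate stands beside the bands. It does not affect the design, the stopping rule or the decision to expand.

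**What to change.** In section 9.1.2, replace the two bands with *any grade (1-5) and grade 3 or higher (3-5)*. State that each patient is counted once, at worst grade, in each of the acute and late windows. Show grade 5 separately as well, so that a death is not merged with non-fatal severe toxicity. The worst-grade rule also removes the dependence on whether an escalating event left an earlier entry.

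The cost is one line of wording, carried into the SAP. It needs no new data and changes neither the sample size nor treatment. The only downside is that the reported severe rate may look less favourable if a fatal toxicity occurs.

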4.4.2 Follow-Up for Discontinued Pembrolizumab without Disease Progression

Patients who discontinue pembrolizumab for any reason other than disease progression will move into the follow-up phase and should be assessed every 9 weeks (63 ± 7 days) and by radiologic imaging as per standard of care to monitor disease status. Every effort should be made to collect information regarding disease status

until the start of new anti-cancer therapy, disease progression, death, withdrawal or end of the study. Information regarding post-study anti-cancer treatment will be collected if new treatment is initiated.

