4.4.3 Survival Status Follow-Up Phase

Once a patient experiences confirmed disease progression or starts a new anti-cancer therapy, the patient moves into the survival follow-up phase and will be followed up every 12 weeks to determine their disease status. This will be done by reviewing their medical notes and/or contacting the patient or GP directly. Patients will remain on this follow-up until death, withdrawal of consent, or the end of the study, whichever occurs first.

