6.2.4 Subsequent Anti-Cancer Therapy Status

Patients that discontinue from pembrolizumab for any other reason than disease progression will have a follow-up visit every 9 weeks in which the Investigator should review all new anti-cancer therapy initiated after the last dose of pembrolizumab. If a patient initiates a new anti-cancer therapy within 30 days after the last dose of trial treatment, the 30 day Safety Follow-up visit must occur before the first dose of the new therapy. Once new anti-cancer therapy has been initiated the patient will move into survival follow-up.

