6.3.11.2 Timing of Disease Assessment

Tumour imaging will be performed by CT. The initial tumour imaging will be performed no more than 28 days prior to confirmation of eligibility. Scans performed as part of routine clinical management are acceptable for use as the screening scan if they are of diagnostic quality and performed within the correct time window.

On-study imaging will be performed at screening every 3 cycles (every 9 weeks) for the first 6 months (\pm 7 days) then every 12 weeks after 6 months (\pm 7 days), and should follow calendar days and should not be adjusted for delays in cycle starts or extension of pembrolizumab cycle frequencies. Tumour imaging and assessment per local standard of care should be performed for patient management and may include additional imaging (e.g. bone scan). Imaging should continue to be performed until documented disease progression, the start of new anti-cancer treatment, withdrawal of consent, death, or the end of the study, whichever occurs first.

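### PFS and DOR are censored at last follow-up although scans stop at new anti-cancer therapy, and PFS/OS have no time zero for patients treated but never irradiated

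*Protocol*

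**What the plan says.** Section 9.1.2 fixes origin, event and censoring for all three time-to-event endpoints.

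- PFS is defined by this interval: "start of radiotherapy until radiological or clinical evidence of progression or death and will be censored at date of last follow-up for surviving patients".
- For OS: "OS will be measured from the start of radiotherapy until death and will be censored at date of last follow-up for surviving patients".
- For DOR: "Duration of response (DOR) will be measured from the date of first response until radiological or clinical evidence of progression or death". The same censoring at last follow-up applies.
- Rates at 6 and 12 months are to be reported for all three, with Parts A and B combined.
- ORR and DCR, in the same section, "will be calculated as a proportion of total treated with a 95% confidence interval".

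On assessment, section 6.3.11.2 states: "Imaging should continue to be performed until documented disease progression, the start of new anti-cancer treatment" (or withdrawal, death or end of study). For patients off drug without progression, section 4.4.2 asks for disease status "until the start of new anti-cancer therapy, disease progression, death, withdrawal or end of the study". Section 6.2.4 adds: "Once new anti-cancer therapy has been initiated the patient will move into survival follow-up".

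Section 4.2 gives pembrolizumab on C1D1 and SBRT on C1D15, C1D17 and C1D19. Section 5.3 provides for removing, and possibly replacing, a patient found to have active pneumonitis on the first day of radiotherapy, which is after the first pembrolizumab dose.

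**The concern.** A progression endpoint is only as good as the assessments behind it. If the censoring date can fall after the last date on which progression was looked for, the interval between them is counted as progression-free without evidence. Here that interval opens whenever a patient starts another anti-cancer treatment without documented progression, for example after stopping pembrolizumab for toxicity. The error goes one way: PFS and DOR rates can only be raised.

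The time origin raises a separate question of population. A patient who receives pembrolizumab and then dies, progresses clinically or is removed before C1D15 belongs to the treated population used for ORR and DCR, but cannot be placed on the PFS or OS time axis.

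PFS at 6 and 12 months is a named secondary endpoint of a single-arm trial. Readers will set it against outside figures, and no control arm shares the bias.

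**Working it through.** **Reproduction.** The protocol states no assumed PFS, OS or event count, so there is no figure to reproduce. The check compares the sections and then sizes the effect under stated assumptions.

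**Censoring: the sections side by side**

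1. Section 9.1.2 censors survivors at last follow-up and mentions neither the last tumour assessment nor new therapy.
2. Sections 6.3.11.2 and 4.4.2 stop imaging and disease-status collection at new therapy; section 6.2.4 then moves the patient to survival follow-up.
3. Section 4.4.3 says such patients "will be followed up every 12 weeks to determine their disease status", using medical notes or contact with the patient or GP; the Trial Summary and section 6.1 agree on disease status, and 6.1 allows telephone contact. Section 6.2.5 lists only patient status, death and loss to follow-up, and section 7.8.1 calls the contacts survival status assessments.
4. Each contact is a follow-up date, so it moves the censoring date forward with no protocol scan due.

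**Size of the censoring effect (illustration)**

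Inputs from section 2.2.2: median PFS 2.8 and 6.3 months; post-switch median survival 9.6 months (range 7.3–10.9), borrowed from the second-line OS figures. Assumptions not in the protocol: a share p = 10–30% switches before progression (about 2–5 of 18), hazards are constant, and a fraction c of later progressions is captured.

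Let λ = ln 2 / median PFS, σ = λ·p/(1−p), so that σ/(λ+σ) = p, and δ = ln 2 / post-switch median survival. With c = 0 the reported curve is

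S(t) = e^(−(λ+σ)t) + σ·[e^(−δt) − e^(−(λ+σ)t)] / (λ+σ−δ),

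that is, patients neither progressed nor switched, plus switchers still alive. With capture it becomes (1−c)·S(t) + c·e^(−λt). The true value is e^(−λt).

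Example (median 2.8, p = 30%, 12 months): λ = 0.2476, σ = 0.1061, δ = 0.0722. Then S = 0.014 + 0.377 × (0.420 − 0.014) = 0.167, against e^(−0.2476×12) = 0.051.

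| Median PFS | Time | True | c = 0; p = 10/20/30% | c = 0.5; p = 10/20/30% |
|---|---|---|---|---|
| 2.8 mo | 6 mo | 22.6% | 25.4/28.5/31.9% | 24.0/25.6/27.3% |
| 2.8 mo | 12 mo | 5.1% | 8.9/12.8/16.7% | 7.0/8.9/10.9% |
| 6.3 mo | 6 mo | 51.7% | 52.1/52.7/53.3% | 51.9/52.2/52.5% |
| 6.3 mo | 12 mo | 26.7% | 27.7/28.8/30.1% | 27.2/27.8/28.4% |

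Over post-switch survival medians of 7.3–10.9 months, the 12-month values with c = 0 span 8.0–18.0% and 27.1–31.0%.

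A second model tests dependence on these choices: 18 patients, about 22% actually switching, death a median of 6 months after progression, no capture. At 12 months the stated rule gives 14.1% against a true 5.2% (median 2.8), and 38.8% against 31.9% (median 7.3, the longest PFS in section 2.2.2). The largest excess is at 6 months with median 2.8: 33.6% against 22.8%, about 11 points. With full capture the excess is zero.

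For scale, the binomial SE at n = 18 is √(0.05×0.95/18) = 5 points and √(0.27×0.73/18) = 10 points.

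**Time origin**

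C1D1 to C1D15 is 14 days, or 0.46 months. Expected deaths in that window at median OS 9.6 months: 1 − 2^(−0.46/9.6) = 3.3%, × 18 = 0.6. Expected PFS events: 4.9% × 18 = 0.9 (median 6.3) to 10.8% × 18 = 1.9 (median 2.8). No tumour CT is due before about week 9, so only death or overt clinical progression could count: about 0–2 patients. If one or two of 18 treated patients were never irradiated and failed early, a 50% rate among the irradiated would be 50% × 17/18 = 47.2% or 50% × 16/18 = 44.4% among all treated. The later origin does not itself raise the rates: it shortens every irradiated patient's time, and under a constant hazard the landmark rates are unchanged.

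**The case against.** Three sections say follow-up after new therapy is for disease status, and clinical progression counts as an event, so a progression recorded in the notes would be picked up without a protocol scan. Counting progression regardless of new therapy is a recognised approach, and the text can be read that way. The 10–30% switching rate has no source in the protocol. Section 2.2.6.2 reports no discontinuations for treatment-related adverse events in the cited pembrolizumab mesothelioma cohort, which had no radiotherapy. At 5% switching (about 1 of 18) and median PFS 2.8 months, the 12-month figure is only 7.0% with no capture, or 6.1% with half, against 5.1%. Radiotherapy start is a defensible origin for an SBRT combination, and section 9.1 says patients without the required safety observations are described separately.

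These points limit the size and make the bias possible rather than certain. They do not remove the defect. Sections 6.2.5 and 7.8.1 do not ask for the disease information that the favourable reading needs, and 12-weekly notes or telephone contact is not equivalent to scheduled CT. Describing never-irradiated patients separately gives them no PFS or OS origin. Because section 9.1.2 states these rules explicitly, they are not details left open for the SAP.

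**Conclusion.** The concern holds on both counts and should be corrected.

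The censoring rule can overstate PFS and DOR. For PFS the excess ranges from zero (full capture) to about 11–12 points in the least favourable cases examined (short PFS, high switching, no capture). In the closed-form model it is 1–3 points at 12 months when median PFS is 6.3 months; the second model gives about 7 points at median 7.3, so a small effect at longer PFS depends on the model. No size was computed for DOR. Switching rates, capture fractions and constant hazards are assumptions.

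The time-origin problem is a population mismatch affecting about 0–2 patients, not an inflation of rates in those irradiated. The endpoints are secondary and descriptive in at most 18 patients; the DLT rule and the sample size are unaffected.

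**What to change.** In section 9.1.2:

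- Censor PFS and DOR at the last adequate tumour assessment before new anti-cancer therapy or loss to follow-up, with one sensitivity analysis counting the start of new therapy as an event.
- Keep OS censored at the date last known alive.
- Measure PFS and OS from C1D1 in all treated patients, keeping the radiotherapy-start version as a supplement.

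Reconcile the Trial Summary and sections 4.4.3 and 6.1 with sections 6.2.5 and 7.8.1 on whether 12-weekly contacts record disease status or survival status only.

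The cost is wording. No patients or data are added, since scan dates and new-therapy information are already collected. PFS may look slightly less favourable. In the second model (about 22% switching, no capture, median 2.8 months), censoring at the last scan gives 21.2% against a true 22.8% at 6 months and 4.8% against 5.2% at 12 months. Some bias remains if switchers progress faster. With 30% switching, twice the progression hazard after the switch and median 2.8 months, censoring at the switch gives 5% against a true 2% at 12 months; the present rule gives 17%.
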